Abstention from Methamphetamine: MUD subjects will be asked to abstain from using methamphetamine on the day of Visit 1 and 2 will be asked to abstain from using methamphetamine for 24 hours prior to Visits 3 and 4. If subjects come to their appointments intoxicated, they may be dropped from the study or rescheduled. **Subject selection and randomization:** [name] laboratory at the Portland VA will genotype the *htaar1* in Part 1 participants to identify all V288V variants (members of the [name] lab may also prep samples but will not read results). The CV Groups will be composed of subjects who are heterozygous or homozygous for the CV SNP without any other variant, while the WT Groups will include those who have the wild type genotype. The *htaar1* gene will also be sequenced in its entirety (the [name] lab will purify the DNA and then send it to the OHSU Core lab) so that individuals with rare non-synonymous *taar1* can be identified *post hoc* and analyzed separately. We will screen subjects until we have 18 subjects in each of the four CV Groups and the WT Groups balanced by age and sex (a research assistant not involved in the subject evaluations will check the balance and will adjust accordingly). As the population gene frequency is 23%, we expect to

Visit Number	1	2	3	4
	Part 1		Part 2	
Informed Consent	\checkmark			
Review Study Eligibility	✓			
Medical History	✓			
Family History	✓			
Neuropsych Assessment		✓		
Computer Tasks		✓		
Vital Signs	✓		✓	✓
Urine Drug Screen/Pregnancy		1		
Test	v	•	v	v
Cheek Swabs	✓			
EKG	✓			
Study Drug or Placebo				
Administered			v	v
MRI Scans			✓	✓
Blood Draw	✓		✓	✓
Saliva Collection	✓		✓	✓
Questionnaires		✓	✓	✓
Total Time (hours)	3	3	8	8

genotype up to 200 individuals to ensure two groups of age and gender matched subjects. We will replace dropouts until we have 18 completers in each group (for a total of 72 completers). The study team will be blind to genotype. The [name] lab will determine genotype and refer subjects back to the study team for inclusion in blocks of six subjects (three CV and three WT). If more than three CV or WT subjects are genotyped before three of the other group, then participants will wait for enrollment into Part 2 until the current block of six subjects is complete. Genotype data will be provided to the pharmacy to allow stratification by genotype during randomization.

Visit Schedule

Part 1: Visits 1 and 2: Consent/Screening: Subjects will be consented and then screened for

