RSFC time courses will also be normalized and detrended, and signals correlated with motion, mean white matter, mean ventricle and mean brain, along with their temporal derivatives, will be removed through linear regression. Motion regression will include 6 parameter displacement time courses plus their derivatives and squares; only frames where displacement is below standard cutoffs will be included in the regression. Postregression time courses will be band-pass filtered between 0.009 and 0.08 Hz. Signal from ventricular regions and from white matter will be removed from the data through linear regression estimations. Specific Outcome Measures and Hypotheses: We will use a mixed effects model with one between-subjects variable (genotype) to investigate outcome variables. Precision brain mapping (Gordon et al., 2017) allows these analyses to occur between subjects with excellent power. SA 1 and Hy 1 predicts a significant effect of genotype on baseline intrastriatal connectivity and craving. Subsequent analyses can be conducted in several ways based on these data. We will use both a hypothesis driven seed region approach based on a priori region of interests (ROIs) of the VS, midbrain, dorsolateral prefrontal cortex, and ventromedial prefrontal cortex and a data driven approach based on a fcMRI correlation matrix. Bivariate correlations between the average BOLD signals from these regions will provide connectivity estimates. In addition to our planned seed-based comparisons, we will secondarily investigate whole brain connectivity with pair-wise correlations between each ROI within the several sets of functionally-defined parcellations and subcortical ROIs. forming correlation matrices. We use ROIs from the highly cited and utilized Gordon Parcellation (Schaefer et al., 2017;Gordon et al., 2016), a set of 333 ROIs supplemented by a set of 19 subcortical regions defined by FreeSurfer (Fischl, 2012) during pre-processing. Correlations will be Fisher's Z transformed to correct for non-normality and to allow averaging across groups. Sub-matrices will be derived using InfoMap and sub-graphs identified with known cerebral networks (Fortunato and Hric, 2016;Rosvall and Bergstrom, 2008). Correlation matrices will provide access to specific circuits within individuals and will be utilized to describe and provide specific predefined network strengths and characteristics (e.g. default-mode, fronto-parietal, dorsal attention and salience attribution), as well as topological properties for each individual and genotype group. Statistical analysis for these effects are modeled after Feczko et al. (2017) and Eggebrecht et al. (2017) and are detailed in 4.4 Statistical Design and Power. Such an approach allows us to consider individual differences in the functional neuroanatomy, as well as investigate genotype-MA interactions. Topological measures include: connection density and strength, network segregation, global efficiency, rich club coefficients, and global segregation; "hub" measurements will include hub degree, strength, within module z-score, and participation coefficient. SA 2 and Hy 2 predicts a significant genotype x acute drug administration interaction, specifically that acute MA administration will have a blunted effect in the CV group. For Hy 2 and Hy 3 our primary analytic model

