Protection of Risks of X-Ray: Only subjects suspected of having a foreign body in their eyes or face will

undergo this procedure. The images will be obtained at the VA clinical imaging center and will be performed by clinical x-ray staff and read by a radiologist.

Protection of Risks of Specimen Collection: Blood will be collected by trained VA phlebotomists to ensure the highest level of safety for subjects.

Potential Benefits of the Proposed Research to Research Participants and Others

This project is not intended to benefit individual subjects but results may help us understand the neurobiology of methamphetamine addiction and potentially help us evaluate future pharmacological treatment approaches for addicted individuals in the future.

Importance of the Knowledge to be Gained

The results of this project will be valuable for understanding genotypic modulation of how addicted individuals respond to MA and informing our understanding of by establishing biomarkers useful in predicting and evaluating treatment response. A predictive model will help individualize relapse risk through a better understanding of neurobiological factors that influence addiction, craving and cognition.

Participation of Non-Veterans

This is an ambitious study and requires recruitment of subjects who are currently experiencing methamphetamine addiction. There are also significant gender effects which necessitate have a gender balanced sample. We will, therefore, need to recruit non-veterans to meet our ambitious recruitment goals and to recruit sufficient numbers of women. Non-veterans may be recruited using flyers posted at OHSU, the Portland VA, local retailers, college campuses, and businesses where social service assistance is provided. Additionally, advertisement will occur on OHSU's Study Participation Opportunities web page, and Craigslist. The Craigslist ad will include a phone number for potential subjects to call and the email response option will be turned off during the generation of the ad. VHA Notice of Privacy Practices (NOPP) us provided to non-veterans and an NOPP acknowledgement is signed.

Data and Safety Monitoring Plans

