Subjects were rated on the PHQ9 (depression), GAD7 (anxiety), FSS (fatigue), BPI severity and intensity (pain), PRMQ (memory), a sleep disturbance scale (P57) and three visual analog scales (VAS) of craving for MA, alcohol or any other drug. Four components from a principal components analysis, which accounted for 80% of the variance, were varimax rotated (**Error! Reference source not found.**). A general linear model (GLM) was calculated with the factor scores as dependent variables and diagnostic group, TAAR1 (WT, at least one CV), a genotype by group interaction term and age, education and sex as covariates. The overall GLM had a significant F with largest effect for Craving. For PC3 (craving response), there was a significant [X^2 (4df) = 15.82, p = 0.003] interaction involving TAAR1 and study group. CS showed no association between

PC3 and TAAR1 (fold change = 0.99, p = 0.94), while the adjusted mean PC3 for MA-ACT and MA-REM groups, with at least one copy of the CV, was estimated to be, 1.55 (95% CI: 1.03 - 2.35; p = 0.036) and 1.77 (95% CI: 0.95 - 3.27; p = 0.071) times the mean response, respectively, for those without the CV. The POLY-REM group evidenced a similar, but non-significant trend; the adjusted mean PC3 for the CV group was estimated to be 1.34 (95% CI: 0.90 - 2.01; p = 0.152) times the adjusted mean response for the WT group. In the POLY-ACT group, the direction reversed, such that the adjusted mean response for the CV group was lower than that of the WT group (95% CI: 0.41 - 0.91; p = 0.016); however, the POLY-ACT group was limited to only three participants without the CV (Figure 2,**Error! Reference source not found.**).

[figure not shown]
Further analysis revealed that the TAAR1 genotype effects in the MA-ACT and MA-REM groups (i.e., 1.55- and 1.77-fold increases) did not differ significantly [X^2 (1df) = 0.11, p = 0.75],

implying a shared underlying effect on craving for those with MUD. Having at least one copy of the TAAR1 CV SNP was associated with a 1.68 (95% CI: 1.14 - 2.47, p = 0.009) fold increase in the adjusted mean craving response as characterized by PC3. Thus, MUD participants with the CV reported higher craving than WT participants.

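### The baseline CV v WT comparison (SA 1/Hy 1) leaves out age and sex, the two factors on which enrolment balances the groups

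*Combined protocol and SAP*

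**What the plan says.** **Balancing.** Under Subject selection and randomization, screening continues until there are 18 subjects "in each of the four CV Groups and the WT Groups balanced by age and sex". A research assistant who does not evaluate subjects checks the balance and adjusts it. The same section plans genotyping "to ensure two groups of age and gender matched subjects", and says "We will replace dropouts until we have 18 completers in each group". CV and WT subjects enter Part 2 in equal numbers, three of each per block of six.

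**Reason for balancing.** Participation of Non-Veterans states: "There are also significant gender effects which necessitate have a gender balanced sample". The Women and Minorities paragraph is softer and says only that such effects may be prominent.

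**Models.** Specific Outcome Measures and Hypotheses opens its modelling text with: "We will use a mixed effects model with one between-subjects variable (genotype) to investigate outcome variables". For Hy 2 and Hy 3 it adds scan day and drug as within-subjects factors, with genotype and the interaction as predictors. Neither description lists age or sex as a covariate. Sex appears only in a post hoc sex by genotype analysis, to be done as necessary. Age does not appear. For the statistical detail of the network analyses the section points to a section 4.4 on statistical design and power, which is not in the document.

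**Precedent.** The preliminary craving model (Preliminary Studies, PS1) included "a genotype by group interaction term and age, education and sex as covariates".

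**The concern.** When groups are balanced on a prognostic factor, the difference between them is estimated more precisely, because that factor can no longer differ by chance between the groups. An analysis that omits the factor does not credit this gain. The factor's variance stays in the residual, the reported standard error exceeds the true sampling variability, and the test is conservative.

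At stake is the SA 1 contrast in the MUD groups: baseline RSFC and craving, CV v WT, with 18 subjects per cell. At that size a few points of power matter.

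There is a second issue. Genotype is not randomised, and balance is kept by hand. A separate biorepository cohort joins the analysis (Biorepository Data/Specimen Use) with no balancing described. Where balance is imperfect, an unadjusted contrast carries part of any age or sex difference into the genotype effect.

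**Working it through.** **Inputs from the documents.** 18 completers per cell; 1:1 CV to WT; four cells, 4 x 18 = 72, which agrees with the stated total. No alpha, power, effect size or SD is given, nor the variance explained by age and sex, so there is no power figure to reproduce.

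**Assumptions.** Two-sided alpha 0.05; true difference d = 0.8 SD; age and sex balanced (exactly so in the simulations); their joint share of outcome variance, R², from 0 to 0.30.

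**1. Standard error.** Relative to an adjusted analysis, the unadjusted standard error is too wide by 1/√(1 − R²). This gives 1/√0.90 = 1.054, 1/√0.80 = 1.118 and 1/√0.70 = 1.195.

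**2. Power.** Unadjusted: noncentrality 0.8 x √(18/2) = 2.40 on 34 df, power 0.645. Adjusted: noncentrality 2.40/√(1 − R²) on 32 df.

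**3. Test size.** Simulated with age and sex exactly balanced and both omitted (40,000 runs per setting).

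| R² | SE too wide by | Size, unadjusted | Noncentrality, adjusted | Power, adjusted |
|---|---|---|---|---|
| 0 | 0% | 0.051 | 2.40 | 0.643 |
| 0.10 | 5% | 0.039 | 2.53 | 0.689 |
| 0.20 | 12% | 0.029 | 2.68 | 0.740 |
| 0.30 | 20% | 0.020 | 2.87 | 0.794 |

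With both covariates in the model the simulated size is 0.050 to 0.051 throughout. At R² = 0.20 the mean reported standard error without adjustment is 0.333, against a true sampling SD of 0.299; with adjustment it is 0.296. Simulated unadjusted power at d = 0.8 is 65% to 66% over the range, so the loss is about 4, 8 to 9 and 13 points at R² = 0.10, 0.20 and 0.30.

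**4. Sensitivity to the effect size.** The difference detectable with 80% power at 18 v 18 (normal approximation) is (1.96 + 0.84) x √(2/18) = 0.93 SD. At d = 0.934, simulated power rises with adjustment from 0.785 to 0.800 (R² = 0.05), 0.784 to 0.816 (0.10), 0.795 to 0.858 (0.20) and 0.813 to 0.901 (0.30). At R² = 0 it is 0.777 v 0.776, so adjusting for irrelevant factors costs almost nothing.

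**5. Hy 2 and Hy 3.** These hypotheses rest on genotype x drug. For each subject take the difference MA minus placebo. Age and sex effects on the subject's level are in both terms and cancel. Simulated at 18 v 18 with a 0.8 interaction and R² = 0.30, the standard error is 0.296 with or without age and sex, and power is 0.743 v 0.741. Omission costs nothing here unless age or sex changes the response to the drug.

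**6. Imperfect balance.** The bias in the unadjusted contrast is the covariate's effect times the difference in its mean between CV and WT. It is zero under exact balance. Its size otherwise cannot be given, because neither quantity is in the documents.

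**The case against.** The strongest case against is as follows.

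- **The size is assumed.** This stands. No R² is given. At 0 there is no gain, and at 0.05 it is about 1.5 points at d = 0.934. The statement on gender effects is made to justify recruiting non-veterans and names no outcome, and nothing says that age affects any outcome.
- **The pilot precedent is partial.** This stands. PS1 adjusted a craving model; the RSFC pilot (PS2) reports no age or sex covariates. The precedent supports the craving half of Hy 1 only.
- **The full statistical section is not available.** This stands as a limit on confidence. Section 4.4 might list covariates, and naming one between-subjects variable may describe only the design factor. The point therefore concerns the model text that can be read.
- **The two harms do not occur together at full strength.** This is correct. The small test sizes need near-exact balance, and they move back toward 5% as balance weakens. Weak balance is then itself a reason to adjust.
- **The error is conservative.** This is correct under balance: there are no extra false positives and no bias, only lost efficiency.

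A reader might infer that every genotype test in the plan has too wide a standard error and too little power. The documents do not support that. Hy 2 and Hy 3 are within-subject interaction tests, from which age and sex main effects cancel, and nothing shows that either factor modifies the drug response. Nor is sex wholly ignored, since a post hoc sex by genotype analysis is planned; that analysis does not adjust the main contrast.

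**Conclusion.** The point holds for SA 1/Hy 1 only. The groups are balanced on age and sex, and the stated baseline model contains neither. If these factors are prognostic, the baseline CV v WT test is conservative and loses power: about 4 points if they explain 10% of variance and about 13 if they explain 30%, at d = 0.8 and 18 v 18, with smaller losses at larger d. If they explain nothing, nothing is lost by omitting them and almost nothing by including them. These figures rest on an assumed R², alpha and effect size, and on near-exact balance. Where balance fails, or the biorepository cohort enters unbalanced, the unadjusted contrast may also be biased, by an amount the documents do not allow one to compute. Confidence is limited by the absence of section 4.4. The change is worth making because the possible gain is useful at this sample size and the cost is close to nil.

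**What to change.** Prespecify age (continuous) and sex as fixed effects in the SA 1 baseline models for RSFC and for craving, with the adjusted genotype contrast as the main result. Apply the same adjustment when biorepository subjects are included; age and sex are among the demographics listed for the shared repository data. Reconcile this wording with section 4.4, or include that section in the document.

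No change is required for Hy 2 and Hy 3. Drug x age and drug x sex terms may be added as sensitivity analyses if the team expects either factor to alter drug response. Sex x genotype stays exploratory.

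The cost is a change of wording and 2 degrees of freedom in SA 1 (34 to 32 at 18 v 18). It needs no new data.

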Part 2: Visits 3 and 4: Scan Days: All study procedures will happen at the Portland VA except for the MRI scans which will take place at the OHSU AIRC. MA administration and questionnaires may take place at either the VA or OHSU. Subjects are asked to abstain from MA for 72 h before the scan. A urinalysis will be performed to ensure that women are not pregnant and that no other drugs are present. Subjects will undergo a baseline MRI scan approximately 1 hour after the start of each visit followed by drug administration (placebo or MA) and a second scan 1.5 hours after that. Blood samples (3 mL) and/or oral fluid samples will be drawn before drug administration and after the second scan to quantify MA levels. At the Portland VA, during visit 2, up to 15 mL blood will be drawn and a cheek swab will be taken and both will be stored in the MARC biorepository located at the Portland VA. Blood may be stored as plasma or whole blood. Surveys and neurocognitive assessments will be performed before and after each scan at the Portland VA. Pulse, respiration, and pulse oximetry will be monitored throughout each scan. Each visit will last approximately 8 hours, and the subjects will be monitored (blood pressure, heart rate) closely throughout. The Systematic Assessment for Treatment Emergent Effects (SAFTEE) will be used to screen for adverse effects at the end of the day and the individual will be provided with discharge instructions in both verbal and paper form, which informs the subjects that these medications have the potential to impair driving and operation of heavy equipment. Subjects will be given a list of drugs that should be avoided for their interactive potential with MA and will be provided with a phone number to call [name] with questions. A break of at least two days will be required between visits to allow washout. Subjects will be required to take public transit or have a designated driver for each visit. Subjects may be offered a meal from OCTRI nutrition services, snacks or gift card to the VA canteen during each of these visits. Subjects may be asked to be a backup subject for Visits 3 or 4. Double-booking will help ensure the best use of time and resources. If both participants show up for the visit and we do not complete your visit, they will be paid \$50 in prepaid debit cards for your time.

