Risks of MRI: Subjects who are claustrophobic may become frightened in the MRI machine. Subjects with metal fragments, wire sutures, staples, implanted pacemakers or defibrillators or metal fragments from welding or shrapnel from combat are at risk from damage due to movement or heating of metal fragments in the 3T magnetic field. Participants will be systematically assessed for ferromagnetic metallic foreign bodies and excluded if there is any doubt. Rarely, subjects experience vertigo, a metallic taste or muscle stimulation. Although none are currently known, there may be unknown risks to fetuses in from the MRI procedure and so pregnant women are excluded.

Risks of Methamphetamine Administration: MA has a high potential for abuse and dependence with continual use. Hypersensitivity reactions are known and include angioedema and anaphylactic reactions. Sudden death, stroke, and heart attack have been reported with use of high doses of methamphetamine and other stimulants. According to FDA-approved Desoxyn® labeling, adverse events include: elevation of blood pressure, tachycardia and palpitation, psychotic episodes, dizziness, dysphoria, overstimulation, euphoria, insomnia, tremor, restlessness, headache, exacerbation of motor and phonic tics and Tourette's syndrome, diarrhea, constipation, dry mouth, unpleasant taste, gastrointestinal disturbances, urticarial, impotence and changes in libido, frequent or prolonged erections, rhabdomyolysis, suppression of growth in children, and alopecia. Stimulants can cause teratogenic and embryocidal effects during pregnancy and amphetamines can be excreted in human milk. Our subjects typically self-administer much higher doses of MA than are used in this study.

NIDA guidelines for administering abusable substances to individuals currently addicted to drugs:

1) A serious and concerted effort be made to link these individuals to drug abuse treatment. We will engage participants (all of whom will be current MA users and meet criteria for MUD) in education about MA addiction and we will offer referral to VA or community treatment at each visit.

2) Inclusion of medical examination and screening to assure the absence of any medical or mental condition for which further drug exposure would be contraindicated. This examination will be performed at the initial visit and subjects will be excluded for co-morbid medical or psychiatric conditions that contraindicate low doses of MA.

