Protection of Risks of Questionnaires, Computer Tasks and Cognitive Testing: Subjects or study staff will terminate questioning or task performance at any time that the subject becomes upset or overly frustrated and does not wish to continue.

Protection of Risks of MRI: Subjects are interviewed extensively to screen for any contraindication to MRI, e.g., surgical aneurysm clips, pacemaker, prosthetic heart valve, neuro-stimulator, implanted pumps, cochlear implants, metal rods, plates or screws, previous surgery, hearing aids, history of welding, metal shrapnel or tattoos with ferro-magnetic particles. If there is any doubt, the subject will be excluded. The research team will obtain orbital x-rays if subjects have any history of welding, grinding or other exposure to metallic particles that could lodge in the eye. Pregnant women (negative urine pregnancy test required before the scan), because of the unknown risk to the fetus, will also be excluded. Participants will be taken to a mock MRI prior to the procedure if they are concerned about claustrophobia. If a subject becomes frightened during the procedure it can be terminated immediately.

Protection of Risks of Methamphetamine Administration: The study team will thoroughly screen potential participants for medications and conditions which would contraindicate use of stimulants. This will include a medical history, family medical history and a brief physical performed by a study physician. Women will be screened for pregnancy at the beginning of each visit and will be removed from the study if found to be pregnant. After the administration of MA, subjects will be continuously monitored for blood pressure and heart rate changes by research staff and during the MRI. Participants will complete a safety questionnaire before they can leave the lab after MA administration and will not be allowed to drive on study visits where MA may be administered.

Protection of Risks to Confidentiality: Study data will be coded and kept separately from any HIPAA Identifiers. Paperwork will be kept in locked cabinets in a locked office at the Portland VA. Digital data, including the spreadsheet linking the subject ID to personally identifiable information, will be kept behind password protected applications and spreadsheets. Data and specimens in the biorepository will not be linked to any personally identifiable data and the code linking spreadsheet will be encrypted once the original study is completed.

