Serum, leukocytes (from whole blood samples) and a buccal swab will be obtained (via separate permission on the HIPAA and ICF), linked to study data for coded storage in the MARC Translational Service Core Biorepository ([name], Administrator). No PHI will be stored in the data repository. Banked contact information

Subjects will be asked to have the following information collected for a contact repository: contact information, date of birth, gender, Veteran status, smoking status, substance use information, mental health status and previous participation in a [name] lab research study. This will be used to contact subjects who may be eligible for future studies with the [name] lab. Subjects will sign an addendum to the VA ICF if they consent to having their information stored for future contact, which is optional. Information will be contributed to the [name] Lab Contact Information Data Repository (mIRB 4512, [name], PhD Administrator).

Oversight

IRB-approved study staff will ensure that any protocol deviations or adverse event will be reported immediately to the PI, who will examine the patient and determine if any additional evaluation or treatment is needed. The PI will ensure that significant adverse events are properly reported to the IRB (within 5 days to comply with VA policy). The [name] Lab will examine all cumulative adverse events semi-annually to determine if there are any systematic problems. OHSU's IRB3 will oversee the study and will be the sole source for study documentation and approval.

Inclusion/Vulnerable Populations

Women and Minorities: Given that gender effects may be prominent in this population, it is important that the ratio of male/female subjects approach 50/50. We will recruit outside of the VA SATP to ensure that women are represented equally with men, in alcohol detox and treatment centers in the Portland area. Minority subjects will be recruited to be a representative cross section of the Portland, Oregon population. That population is primarily Caucasian 82.4%, with 7% African-American, 7%, Asian, 1.8% Native Hawaiian or Other Pacific Islander, and 1.8% Native American. Additionally, the population will be primarily non-Hispanic 93%, with 7% Hispanic.

Children: Children will be excluded from this study.

Prisoners: No prisoners will be included. If subjects are incarcerated during their enrollment, they will be dropped from the study. Potential subjects will not be in any formal treatment program.

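### Adverse events are actively solicited only before discharge on each dosing day; nothing is scheduled afterwards, so delayed effects such as insomnia rest on spontaneous report or an unstated SAFTEE look-back

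*Combined protocol and SAP*

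**What the plan says.** Two instruments ask about adverse effects, both on the dosing day. Under Part 2: Visits 3 and 4: Scan Days, SAFTEE "will be used to screen for adverse effects at the end of the day". Under Protection of Risks of Methamphetamine Administration, "Participants will complete a safety questionnaire before they can leave the lab after MA administration". During the visit itself, "the subjects will be monitored (blood pressure, heart rate) closely throughout".

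After discharge there are passive routes. The subject "will be provided with a phone number to call" with questions. The Oversight section requires that "any protocol deviations or adverse event will be reported immediately to the PI", and says that the laboratory "will examine all cumulative adverse events semi-annually to determine if there are any systematic problems".

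The visit schedule table has four visits, no adverse-event row, and no follow-up visit or call. Between the dosing visits, "A break of at least two days will be required between visits to allow washout". The labelled effects listed under Risks of Methamphetamine Administration include "overstimulation, euphoria, insomnia, tremor, restlessness".

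**The concern.** Sleep after a daytime dose can be reported only the next day, once both same-day instruments are complete. The protocol sets time aside for washout between visits, so it treats the drug as still relevant after the subject goes home. Yet it plans no question about that interval. The cumulative review can work only with events that reach staff.

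At stake is the completeness of the safety record. Effects that appear during the visit are asked about systematically. Those that appear later depend on whether the subject thinks to mention them, so the two kinds of event are not recorded on the same footing. The point applies to controls as much as to users. Half of the planned completers are controls, whose entry criterion is a single past stimulant exposure, so the protocol's reassurance that subjects habitually take much larger amounts does not cover them.

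**Working it through.** The plan states no figure for this point, so there is none to reproduce. The check is a reading of the schedule, safety and oversight sections, with simple arithmetic on timing and order.

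**1. How long after the dose is the subject observed?** Inputs from the Scan Days section: the visit lasts about 8 h, the baseline scan starts about 1 h in, and the drug follows that scan. From MRI Acquisition: at least 40 min of usable data per run.
- Earliest dose time = 1 h + 40 min = 1 h 40 min (about 1.67 h).
- Longest post-dose observation = 8 h − 1 h 40 min = 6 h 20 min, or about 6.3 h.

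Setup time and frames lost to motion make it shorter. Clock times are not given. I assume a daytime visit: any start up to noon ends by 20:00 (12:00 + 8 h). SAFTEE is then finished before the first night and cannot capture that night's sleep on the day it is given.

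**2. How many completers receive MA at the last dosing visit?** Inputs: 4 groups × 18 = 72 completers. From MA Administration and Randomization, three of every six subjects take MA at the earlier dosing visit and three at the later one.
- 72 ÷ 6 = 12 blocks.
- 12 × 3 = 36 completers with MA at the later visit.

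The figure is approximate because dropouts are replaced and final order balance among completers is not guaranteed. It also needs one reading of the text. The randomization paragraph calls the two MA occasions visits 2 and 3, whereas the schedule table and the Scan Days section place study drug at Visits 3 and 4. I take them as the first and second dosing visits. Those passages must be reconciled.

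**3. What later opportunity does each half have?**

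| MA given at | Next scheduled contact | Solicited adverse-event question covering the interval |
|---|---|---|
| Visit 3 (about 36) | Visit 4, at least two days later | SAFTEE at the end of Visit 4, look-back not stated; none described before dosing |
| Visit 4 (about 36) | None | None |

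**4. Is there already an occasion to ask?** Yes. Under Appointment Confirmation, staff ask symptom questions on confirmation calls and again at the start of each in-person visit, but the stated content is COVID-19 only.

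**The case against.** A reader might infer that delayed effects cannot be recorded at all, or that nothing is collected after Visit 4. The documents do not support that. The Oversight rule sends any adverse event to the principal investigator, with no cut-off at discharge or at the last visit, and subjects hold a phone number. A volunteered report of insomnia is recordable.

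A reader might also infer that insomnia will appear absent by construction. That assumes SAFTEE asks only about the same day. Its look-back is not stated, and the instrument's source is not available here. SAFTEE at Visit 4 could pick up events since Visit 3 for the half given MA first.

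Nor are subjects dosed unseen at Visit 4. Vital signs, a urine drug screen and surveys come first, and users give a pre-dose sample for MA level. These are not adverse-event questions, but they are contact.

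It is tempting to divide 6.33 h by a 48 h washout and report 13%. That ratio measures no harm: the minimum gap between visits is not a documented risk window, and the result is not a rate of missed events.

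The other side can also say that each subject takes MA once, orally, at 30 mg or less; that twelve healthy controls in the preliminary study tolerated repeated sessions; and that subjective effects peaked one to two hours after dosing, inside the observed period. The graver labelled events come from a general product list, and nothing here shows that they are likely after discharge. The hypotheses concern connectivity, craving, subjective experience and cognition, so no planned inference depends on an adverse-event rate.

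All of this stands and limits the point. It does not close the gap. The phone line is offered for questions, the reporting rule acts only on what staff learn, and the half given MA last has no further scheduled contact. The preliminary study reports six hours of monitoring after its test dose and no follow-up after discharge, so it cannot show that later effects are rare.

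**Conclusion.** The point holds in a limited form. Active solicitation stops at discharge on each dosing day, and no contact is scheduled after Visit 4. Delayed effects that the protocol itself names, insomnia being the clearest, therefore depend on spontaneous report or on a SAFTEE look-back that is not stated, and will probably be under-recorded. About 36 of 72 completers receive MA with no later scheduled contact. For the other 36 or so, capture depends on the unstated look-back.

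This rests on three assumptions: visits take place in the daytime; the 3:3 order carries through approximately to completers; and the randomization paragraph's visit labels mean the two dosing visits. How many events would be missed cannot be computed from the documents. This is a worthwhile improvement to the safety data. It is not an error in the efficacy analysis.

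**What to change.** Four changes, all to data collection:
- Give SAFTEE at the start of Visit 4, before dosing, with a written look-back to discharge from Visit 3.
- Add one brief scripted SAFTEE call after each dosing visit, no earlier than the next morning, with an explicit question on sleep.
- State the adverse-event reporting period, including when it ends after Visit 4.
- Include these data in the semi-annual review described under Oversight.

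Separately, reconcile the visit numbers in MA Administration and Randomization with those in the schedule table and the Scan Days section.

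How clinicians act on what is learned is for the sponsor to decide. The cost is one short questionnaire at an existing visit and two short calls per subject, made by staff who already place confirmation calls. Some subjects will not be reached; recording failed attempts would keep a missing answer from being read as no event.
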